## **2.7 Statistical Analysis**

Since the number of patients for this study is minimal and multiple factors are of concern, descriptive statistics will be used, and the study is expected to be under powered to perform any formal statistical inference. The number, mean, standard deviation, median, interquartile range of the level of the pharmacokinetic parameters of EGCG and 2 of the major metabolites at different time points and the difference from screening to Visit 1, Visit 2 or Visit 4, and the changes in liver function, estrogen levels, endometrial thickness, and follicular measurements will be presented for the three treatment groups, and then stratified by age group and/or the presence or absence of uterine fibroid. For comparison, a two-way ANOVA will be used to compare the effects of the three treatments and the presence of fibroids on the above outcome parameters. With a sample size of 36 patients for the three treatment groups, which includes 18 subjects with uterine fibroids and 18 without uterine fibroids, with an alpha of 0.05, the power of the study would be 0.44 and 0.85 for a medium (0.25) or large (0.4) effect size, respectively. There are insufficient preliminary data

in the literature to support or not support the reasonableness of these effect sizes. For the comparison of serum folate levels among wildtype MTHFR, MTHFR (C677T), and MTHFR (A1298C) patients, ANOVA (unadjusted) and multivariate linear regression will be used.

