### 6.2 Primary Outcome Measurements

The primary outcome parameter will be differences in pharmacokinetic parameters of EGCG and 2 of the major metabolites between the 3 treatment groups.

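### The primary pharmacokinetic comparison states no analysis scale and plans no between-arm exposure ratio with a confidence interval

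*Combined protocol and SAP*

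**What the plan says.** Sections 2.7 and 6.4 hold the whole analysis plan and are close to identical. The summaries are "The number, mean, standard deviation, median, interquartile range of the level of the pharmacokinetic parameters of EGCG" and two metabolites, by time point and as a difference from screening. For the comparison, "a two-way ANOVA will be used to compare the effects of the three treatments and the presence of fibroids" on the outcome parameters. Section 6.2 words the primary outcome as "differences in pharmacokinetic parameters of EGCG and 2 of the major metabolites between the 3 treatment groups"; Section 2.5 is similar.

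The documents nowhere mention a log transformation, geometric mean, geometric CV, exposure ratio or confidence interval. They do not name AUC, Cmax or Tmax either, although Section 4.3.3 plans sampling at 0.5, 1, 2, 4, 6 and 8 hours at Visits 1 and 2, from which these could be derived.

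Both analysis sections call the study descriptive and expect it to be underpowered for formal inference. Sections 4.3.5 and 6.4 exclude women whose screening EGCG level is detectable.

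**The concern.** Section 2.4 says the combination arms exist because clomiphene or letrozole might interact with EGCG. Sections 3.1 and 5.2 say the pharmacokinetics of the combinations are unknown and that the results feed the larger FRIEND study. The useful answer is a factor: how much higher or lower exposure is with each combination than with EGCG alone, and which changes the data rule out.

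The planned outputs do not give that. Means, SDs, medians and IQRs describe each arm separately, and the ANOVA gives a p-value. In a study that expects to be underpowered, a non-significant p-value does not show that there is no interaction, whereas a ratio with its interval shows what remains possible.

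Leaving the scale open adds two smaller problems. The scale of the primary test could be chosen after the data are seen. And if exposure is strongly right-skewed, an untransformed test can be less sensitive.

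**Working it through.** **1. The plan's own figure.** Section 2.7 states that "the power of the study would be 0.44 and 0.85 for a medium (0.25) or large (0.4) effect size, respectively". Reading the effect sizes as Cohen's f, the noncentrality is λ = N·f². With N = 36, λ = 36 × 0.0625 = 2.25 and 36 × 0.16 = 5.76. The treatment test on 2 and 30 df then has power 0.229 and 0.521, so the stated values are not reproduced. N = 72 with 2 and 66 df (λ = 4.5 and 11.52) gives 0.443 and 0.853, which matches both. That is a separate matter and nothing below depends on it. What matters here is that f is in SD units and carries no scale, so the plan's power statement cannot be read as a fold change.

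**2. Inputs for the check.**
- From the documents: 36 women, three equal arms (12 each), 18 with and 18 without fibroids, alpha 0.05.
- Assumed: 6 women per treatment-by-fibroid cell, lognormal data, and between-subject CV from 30% to 100%.

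**3. Precision of a geometric mean ratio.** The log-scale SD is s = √ln(1 + CV²). For 12 against 12 with 30 error df, the 90% half-width on the log scale is 1.697 × s × √(2/12). If the true ratio is 1:

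| CV | s | half-width | 90% CI for the ratio |
|---|---|---|---|
| 30% | 0.294 | 0.203 | 0.82 to 1.23 |
| 50% | 0.472 | 0.327 | 0.72 to 1.39 |
| 80% | 0.703 | 0.487 | 0.61 to 1.63 |
| 100% | 0.833 | 0.577 | 0.56 to 1.78 |

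Even at CV 100% the interval would exclude both a halving and a doubling when the point estimate is 1.

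**4. Power of the treatment F test, untransformed against log scale.** I simulated 100,000 balanced 3 × 2 trials per scenario, with one arm differing from the other two by the factor shown. Entries are percentages, untransformed / log:

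| CV | no effect | halved | doubled | ×1.5 |
|---|---|---|---|---|
| 30% | 4.9 / 5.0 | 100 / 100 | 100 / 100 | 92.3 / 92.4 |
| 50% | 4.6 / 5.0 | 88.9 / 95.1 | 93.9 / 95.2 | 50.9 / 53.2 |
| 70% | 4.2 / 4.9 | 58.0 / 75.7 | 70.6 / 75.8 | 28.6 / 32.2 |
| 80% | 4.2 / 5.1 | 45.3 / 65.5 | 58.6 / 65.6 | 22.5 / 26.6 |
| 100% | 3.8 / 5.0 | 29.2 / 50.5 | 41.1 / 50.5 | 15.5 / 19.8 |

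The gain from the log scale is nil at CV 30% and about 1 to 6 points at CV 50%. At CV 70 to 100% it is 18 to 21 points for a halving, 5 to 9 for a doubling and about 4 for a 1.5-fold rise. Dropping the interaction term (32 error df) changes no power figure by more than 0.5 points.

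**5. The reference for change.** The plan summarises differences from screening, but eligible women have undetectable EGCG then, so a log change from screening is undefined. Screening also has no 8-hour profile; Section 2.4 plans those only at Visits 1 and 2. All women start EGCG at screening, and clomiphene or letrozole is dispensed at Visit 1 (Section 4.3.3). Visit 1 can therefore serve as the within-woman reference if its sampling comes before the first dose of those drugs. Section 4.3.3 lists the blood tests ahead of dispensing but does not state that order as a rule.

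**The case against.** A reader might infer that the plan has chosen an untransformed ANOVA. The text does not support this. It is silent on scale and excludes nothing, and differences between groups is ordinary wording for any comparison, not a commitment to arithmetic differences. The accurate statement is that no scale is specified.

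A reader might also infer that the planned test is faulty or plainly loses power. That does not stand either. The untransformed test keeps its Type I error at or below 5% (3.8 to 4.9% here), so it is valid and slightly conservative. The power loss depends on a CV that the documents do not give, and on lognormality, which is the case most favourable to the log scale. The large gaps arise only for a fall in exposure at high CV, and at CV 100% the log analysis still has only about 51% power for a halving.

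Finally, the plan disclaims formal inference and already lists the median and IQR, which suit skewed data. This is a good reason not to lead with power. It does not answer the main point: a descriptive study needs an estimate with its precision all the more, and summaries of separate arms do not provide one.

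**Conclusion.** The point holds as a gap in specification and reporting. The primary comparison has no stated scale, no named parameters, and no planned between-arm estimate with an interval. That conclusion rests on the text alone and needs no assumed CV.

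The interval widths and power gains are illustrations under lognormal data, balanced cells and an assumed CV. They use total between-subject variation. If Visit 1 is used as a within-woman reference, the relevant variance is that of the within-woman log ratio, which the documents do not give either. The change would improve the primary analysis appreciably, but the trial is not invalid without it.

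**What to change.** In Sections 2.7 and 6.4, and in the outcome wording of Sections 2.5 and 6.2:

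- Name the parameters taken from the 8-hour sampling, for example AUC, Cmax and Tmax, for EGCG and the two chosen metabolites. Section 4.3.3 lists no pre-dose sample, so the AUC definition should say how the time before 0.5 hours is handled.
- Analyse AUC and Cmax on the log scale in the planned ANOVA with treatment and fibroid status.
- Report geometric means, geometric CVs, and the geometric mean ratio of each combination arm to EGCG alone with a confidence interval. State the level in advance; 90% is a convention, not something the documents require.
- Summarise Tmax by median and range.
- Do not use a log change from screening. Use Visit 1 as the within-woman reference, provided the protocol confirms that its sampling precedes the first clomiphene or letrozole dose.

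The cost is revised analysis wording and a little extra analysis work. No new patients, visits or samples are needed.

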### 2.4 Treatment

The 36 women will be randomized to one of the following groups:

1. EGCG daily alone.
2. EGCG daily with clomiphene citrate 100mg for 5 days.
3. EGCG daily with letrozole 5mg for 5 days.

The purpose of studying EGCG in combination with clomiphene citrate or letrozole is to assess the safety of using them together prior to the initiation of the FRIEND study. It is expected that EGCG will decrease fibroid size and decrease humoral activity leading to improved quality of endometrium for implantation. Clomiphene citrate and letrozole are being used for ovulation stimulation as treatment for unexplained infertility. In view of the possibility of interaction and change in toxicity when both are used together for FRIEND study, it was suggested by our pharmacology reviewer to include EGCG with the addition of clomiphene citrate and letrozole for the safety study.

The initial screening visit will include EGCG levels, liver function, folate and estrogen levels. A genetics sample collection, urine pregnancy test and pelvic ultrasound will also be performed after informed consent. Patient will be given the EGCG (Green Tea extract) to start after the screening visit. Patients will be counseled on dietary restrictions while on EGCG.

Visit 1 will occur on menstrual cycle day  $3 \pm 2$  days. EGCG levels over 8 hours, liver function, and urine pregnancy testing will occur at this visit. Patients will be assigned into their groups and provided with their respective treatments at this visit.

Patient will return between days 8-10 of the cycle for Visit 2. EGCG levels over 8 hours, liver function, estrogen, and urine pregnancy testing will occur at this visit.

The patient will return for Visit 3 between days 14-16 for a pelvic ultrasound evaluation of endometrial thickness and ovarian characteristics.

The final study visit (Visit 4) will be approximately 4 weeks after initiation of the study treatment and will involve EGCG levels, liver function, folate, and urine pregnancy test and pill counts.

The 4 lab panels (screening, Visits 1, 2, and 4) will include EGCG and metabolite analyses, liver panel (AST, ALT, total bilirubin, ALP) and estrogen levels, and a urine pregnancy test. The EGCG analyses at visits 1 and 2 will include testing over 8 hours.

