#### 4.3.3 Study Summary

Recruitment and Prescreening: see Section 5 descriptions following.

Screening visit (anytime in cycle 1):

1. Obtain informed, signed consent.
2. Complete medical/gynecological/menstrual history and physical exam of female study participant.
  - Vital signs, height, weight, hip and abdominal circumference, BMI
  - Pap smear if necessary per current ACOG time-frame guidelines
  - Standard pelvic and breast exam conducted by physician or within past 12 months
3. Perform radiological exams.
  - Pelvic ultrasound measuring uterine and ovarian characteristics or within past 3 months
4. Laboratory tests: EGCG and metabolites, liver function, folate, estrogen levels, genetics sample collection and urine pregnancy test.
5. Dispense Green Tea extract and educate on dietary restrictions while taking Green Tea extract and with the importance of taking food. All patients to start Green Tea extract at this visit.
6. Contraception education. Patients will be counseled to use non-hormonal double-barrier method: a male/female condom plus spermicidal agents, cervical cap, diaphragm or sponge.
7. Concomitant medication collection.

Visit 1 (Day 1-5):

Patient will be seen on menstrual cycle day  $3 \pm 2$  days for clomiphene citrate/letrozole initiation visit

1. Vital signs and weight.
2. Laboratory tests: EGCG levels over 8 hours (0.5,1,2,4,6,8), liver function, folate, estrogen level, and urine pregnancy testing.
3. Concomitant medication collection and pill counts of EGCG.
4. Randomization and dispensation of clomiphene citrate/letrozole.
5. Contraception education. Patients will be counseled to use non-hormonal double-barrier method: a male/female condom plus spermicidal agents, cervical cap, diaphragm or sponge.

Visit 2 (day 8-10):

Patient will return several days after final clomiphene citrate/letrozole administration

1. Vital signs and weight.
2. Laboratory tests: EGCG levels over 8 hours (0.5,1,2,4,6,8), liver function, folate, estrogen level and urine pregnancy testing.

3. Concomitant medication collection and pill counts of EGCG and clomiphene citrate or letrozole as appropriate.
4. Contraception education. Patients will be counseled to use non-hormonal double-barrier method: a male/female condom plus spermicidal agents, cervical cap, diaphragm or sponge.

Visit 3 (day 14-16):

1. Pelvic ultrasound via a transvaginal probe or transabdominal transducer evaluation of endometrial thickness and ovarian characteristics.

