Visit 4 (day 30-35):

Patient will return for final study visit.

1. Vital signs and weight, hip and abdominal circumference, BMI
2. Laboratory tests: EGCG and metabolites, liver function, estrogen level, folate, and urine pregnancy test.
3. Concomitant medication collection. Return unused medications and pill counts of EGCG.

Future Studies: One tube of blood will be collected at each visit to be stored for future analyses related to this study.

*4.3.4 Inclusion Criteria*

1. Healthy women  $\geq 18$  to  $\leq 40$  years of age with or without uterine fibroids
2. Must use a double-barrier method for contraception

*4.3.5 Exclusion Criteria*

1. Subjects using Green Tea/EGCG within 2 weeks prior to study enrollment. Matcha (Japanese green tea), maca powder, green tea beverages and all other forms of green tea require a 2-week wash-out. Patients with a detectable EGCG level at the screening visit will be excluded.
2. Known liver disease (defined as AST or ALT  $>2$  times normal, or total bilirubin  $>2.5$  mg/dL).
3. History of alcohol abuse (defined as  $>14$  drinks/week) or binge drinking of  $\geq 6$  drinks at one time).
4. Subject using hormonal contraceptives: 3-month wash-out is required for all oral or cyclic progestins, GnRH agonists/ antagonists, gonadotropins, injectable contraceptives, oral contraceptives, contraceptive implants and previous use of clomiphene and letrozole.
5. Subjects who are pregnant or breastfeeding
6. Known hypersensitivity to the study drugs
7. Any chronic disease

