### 6.4 Difference in serum folate levels among wildtype MTHFR, MTHFR (C677T), and MTHFR (A1298C) patients. Statistical Analyses

Since the number of patients for this study is minimal and multiple factors are of concern, descriptive statistics will be used, and the study is expected to be under powered to perform any formal statistical inference. The number, mean, standard deviation, median, interquartile range of the level of the pharmacokinetic parameters of EGCG and 2 of the major metabolites at different time points and the difference from screening to Visit 1 or Visit 2 or Visit 4, and the changes in liver function, hormone levels, endometrial thickness and follicular measurements will be presented for the three treatment groups, and then stratified by age group and/or the presence or absence of uterine fibroid. Patients with a detectable EGCG level at the screening visit will be excluded. For comparison, a two-way ANOVA will be used to compare the effects of the three treatments and the presence of fibroids on the above outcome parameters. With a sample size of 36 patients for the three treatment groups, and 18 subjects with uterine fibroids and 18 without uterine fibroids, with an alpha of 0.05, the power of the study would be 0.44 and 0.85 for a medium (0.25) or large (0.4) effect size, respectively. There are insufficient preliminary data in the literature to support or not support the reasonableness of these effect sizes. For the comparison of serum folate levels among wildtype MTHFR, MTHFR (C677T), and MTHFR (A1298C) patients, ANOVA (unadjusted) and multivariate linear regression will be used.

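### PK change is referenced only to screening, which cannot serve as a PK baseline, while the Visit 1 profile and the age stratum are left out of the Visit 2 comparison

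*Combined protocol and SAP*

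**What the plan says.** Sections 2.7 and 6.4 plan summaries of PK levels at each time point and of "the difference from screening to Visit 1, Visit 2 or Visit 4" (6.4: "the difference from screening to Visit 1 or Visit 2 or Visit 4"). No other reference visit is named for PK. The secondary outcome of PK change within each group (2.6, 6.3) names none at all.

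The comparative method is given as follows: "a two-way ANOVA will be used to compare the effects of the three treatments and the presence of fibroids on the above outcome parameters". Age group is a randomisation stratum (2.3, 5.1) but enters only the stratified summaries.

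Four design facts bear on this:

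- **Eligibility (4.3.5, repeated in 6.4):** "Patients with a detectable EGCG level at the screening visit will be excluded".
- **Profiles (2.4):** "The EGCG analyses at visits 1 and 2 will include testing over 8 hours". Section 4.3.3 gives post-dose times of 0.5 to 8 hours at those two visits only.
- **Start of EGCG (4.3.3, screening visit):** "All patients to start Green Tea extract at this visit". Screening may fall anywhere in cycle 1.
- **Allocation:** Section 2.4 says of Visit 1 that "Patients will be assigned into their groups and provided with their respective treatments at this visit". Section 4.3.3 lists the Visit 1 blood tests second and randomisation with dispensing fourth.

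**The concern.** A change score is useful when the reference value carries information about the woman. Screening cannot do that for EGCG, because every eligible woman has an undetectable level. Subtracting it removes no between-woman variation, and a ratio to it is undefined. For parameters that need a concentration–time profile, there is nothing at screening to subtract, for EGCG or for a metabolite. Visit 4 also has no profile.

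Visit 1, by contrast, yields a full profile on EGCG in every arm, apparently before clomiphene or letrozole begins. The plan summarises it but does not use it as a baseline.

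The primary outcome is the between-arm PK difference with 36/3 = 12 women per arm, and the plan describes itself as descriptive and underpowered. What readers will take from it is an estimate and its uncertainty, so precision available from data already collected is worth having. For the within-group outcome the issue is meaning: a change from screening mainly shows that women are now taking EGCG.

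**Working it through.** **Plan's own figures.** The plan gives no interval width, PK variance or correlation between visits. Its only precision figures are power 0.44 and 0.85 for effect sizes 0.25 and 0.4. For the treatment effect with N = 36 (2 and 30 df), recalculation gives 0.23 and 0.52; the stated pair matches N = 72 (0.443 and 0.853). That is a separate question, and nothing below uses those figures.

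**Inputs.** 36 women, three equal arms, 18 with and 18 without fibroids (2.7, 4.3.2), hence 6 per treatment-by-fibroid cell if balanced. Assumed: rho; equal variances at the two visits; age balanced 3/3 within each cell.

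**Planned model.** Treatment × fibroid with interaction has 36 − 6 = 30 error df. The mean 95% half-width for an arm difference in the Visit 2 level, in SD units, is t(30) × √(2/12) × mean of s = 2.042 × 0.408 × 0.992 ≈ 0.827.

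**Adjusted model.** Adding the Visit 1 value and age group leaves 28 error df. With age unrelated to PK:

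width ratio ≈ √(1 − rho²) × √(1 + 1/27) × t(28)/t(30) = √(1 − rho²) × 1.018 × (2.048/2.042) = √(1 − rho²) × 1.021

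Simulation (10,000 to 12,000 trials per rho) agrees. The change-score column is √(2(1 − rho)), for a plain Visit 2 minus Visit 1 difference. All ratios are relative to the planned ANOVA on Visit 2 levels.

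| rho (assumed) | ANCOVA, formula | ANCOVA, simulated | Trials with narrower adjusted interval | Plain change score |
|---|---|---|---|---|
| 0 | 1.021 | 1.021 | 26% | 1.41 |
| 0.2 | 1.001 | 1.000 | 42% | 1.26 |
| 0.3 | 0.974 | 0.973 | 60% | 1.18 |
| 0.5 | 0.884 | 0.883 | 90% | 1.00 |
| 0.7 | 0.729 | 0.729 | 99.5% | 0.77 |

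ANCOVA breaks even where √(1 − rho²) = 1/1.021, at rho of about 0.2. The plain change score breaks even only at rho = 0.5. Coverage of the adjusted interval was 94.7 to 95.2%.

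**On the ratio scale.** With an assumed between-woman CV of 50%, the log SD is √ln(1.25) = 0.472. The unadjusted interval for a ratio against EGCG alone is ×/÷ exp(0.827 × 0.472) = 1.48. Adjusted, it is 1.49, 1.48, 1.46, 1.41 and 1.33 at rho 0, 0.2, 0.3, 0.5 and 0.7. At rho 0.7 it moves from 1.27 to 1.19 if the CV is 30%, and from 1.69 to 1.46 if it is 70%.

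**Variable run-in.** Assuming a 28-day cycle and Visit 1 in the next cycle, time on EGCG before Visit 1 runs from 1 day (screening on day 28, Visit 1 on day 1) to 32 days (screening on day 1, Visit 1 on day 5). If this adds a share v to Visit 1 variance, rho becomes rho/√(1 + v). For v = 25, 50 and 100%:

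- rho 0.7 falls to 0.63, 0.57 and 0.49, with width ratio 0.79, 0.84 and 0.89;
- rho 0.5 falls to 0.45, 0.41 and 0.35, with width ratio 0.91, 0.93 and 0.96.

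**Age alone.** If age group explains 0, 5, 10 or 20% of variance (assumed), adding it gives width ratios of 1.00, 0.97, 0.94 and 0.88. Leaving it out makes the planned interval conservative (coverage 95.0, 95.5, 96.0 and 97.3%).

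**The case against.** The strongest reply is that the primary outcome is a between-arm difference, that levels at each visit are already listed among the quantities to be compared, and that subtracting an undetectable value is redundant rather than harmful. This stands. A reader might infer that the primary comparison is invalid or biased; the documents do not support that, because randomised arms can be compared directly on Visit 2 levels.

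The precision gain rests on a correlation that the documents do not supply. It is nil at 0.2, and at 0.5 the ratio factor moves only from 1.48 to 1.41. The plan also promises no confidence intervals. All of this is fair, and it makes the point an improvement rather than a correction of an error in the comparison.

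A reader might infer that the Visit 1 to Visit 2 change within a combination arm isolates the added drug. It does not: it also carries further time on EGCG and a move from cycle day 1–5 to day 8–10. Only the contrast with EGCG alone separates these.

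A reader might also infer that the protocol contradicts itself on when randomisation occurs, because the schedule in 5.9 appears to mark it under Visit 2. That table is visibly broken as extracted, and 2.4 and 4.3.3 agree on Visit 1. What remains is that neither section says outright that sampling is finished before the first clomiphene or letrozole dose.

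Finally, the plan names no PK parameters. Single concentrations of a metabolite could be differenced from screening, since the exclusion covers EGCG only. The statement that the difference cannot be formed is therefore limited to profile-based parameters.

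**Conclusion.** The point holds as a cheap improvement. Two parts need no assumption: for EGCG the difference from screening is simply the later value, and for profile-based parameters of any analyte it cannot be formed. The within-group secondary outcome therefore has no workable reference visit for those parameters.

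The between-arm comparison is sound as planned but may be less precise than it could be. Adjusting for Visit 1 and age group would narrow intervals by about 12% at rho 0.5 and 27% at rho 0.7, less if run-in varies, with no gain at rho 0.2 or below. These figures assume balanced cells and equal variances, and that the Visit 1 profile is completed before clomiphene or letrozole starts. The break-even near 0.2 belongs to ANCOVA only.

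**What to change.** 1. State in the protocol that the Visit 1 8-hour profile is completed before the first clomiphene or letrozole dose, if that is the intended order, and check that 2.4, 4.3.3 and 5.9 agree.
2. If it is, compare arms on log Visit 2 PK parameters by ANCOVA, adjusting for the Visit 1 value of the same parameter, fibroid status and age group. Report geometric mean ratios against EGCG alone with 95% confidence intervals, and days on EGCG before Visit 1 by arm.
3. If it is not, adjust for fibroid status and age group only, because a Visit 1 value affected by treatment could absorb part of the effect.
4. Use Visit 1, not screening, as the reference for within-group change in profile-based parameters, and interpret that change against the EGCG-alone arm.
5. Name the PK parameters and the two metabolites, so that these rules can be applied.

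The cost is two error degrees of freedom: intervals about 2% wider if neither covariate predicts PK. No new samples are needed. Apart from the protocol statement in step 1, this is analysis-plan wording.

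The visit for the follow-up endometrial scan (Visit 3 in 2.4 and 4.3.3, Visit 2 in 5.7) is a separate matter and should be reconciled separately.

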## **2.6 Secondary Outcome Parameters**

The secondary outcome parameters will include:

- Changes in liver function between the 3 groups.
- Changes in estrogen levels (E2) between the 3 groups.
- Changes in endometrial thickness and ovarian characteristics between the 3 groups.
- Change in the pharmacokinetic parameters of EGCG and metabolites within each group.
- Difference in serum folate levels among wildtype MTHFR, MTHFR (C677T), and MTHFR (A1298C) patients.

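### The estradiol change compared between arms has no named baseline or end visit, and a change built on screening or Visit 4 would carry menstrual-phase variance that adjusting Visit 2 for Visit 1 avoids

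*Combined protocol and SAP*

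**What the plan says.** Section 2.6 lists as a secondary outcome "Changes in estrogen levels (E2) between the 3 groups". Section 2.7 describes the summaries in one long sentence: "the difference from screening to Visit 1, Visit 2 or Visit 4, and the changes in liver function, estrogen levels", and so on. In that sentence the difference from screening belongs to the pharmacokinetic parameters of EGCG and its metabolites. The estrogen changes come in a separate clause, "and the changes in liver function, estrogen levels, endometrial thickness, and follicular measurements will be presented for the three treatment groups", that names no baseline and no end visit. Section 6.4 has the same structure: "the difference from screening to Visit 1 or Visit 2 or Visit 4, and the changes in liver function, hormone levels". Both sections then apply a two-way ANOVA with treatment and fibroid status as factors. Neither gives a baseline covariate or a term for cycle day.

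Section 4.3.3 sets the sampling:

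- **Screening** is headed "Screening visit (anytime in cycle 1", and its tests are listed as "Laboratory tests: EGCG and metabolites, liver function, folate, estrogen levels, genetics sample collection and urine pregnancy test". All women start green tea extract at this visit.
- **Visit 1** is on cycle day 3 ± 2 and includes "liver function, folate, estrogen level, and urine pregnancy testing". Randomization and dispensing of clomiphene or letrozole come later in the same visit list.
- **Visit 2** is on cycle day 8-10 and also includes estrogen.
- **Visit 4** is on day 30-35: "Laboratory tests: EGCG and metabolites, liver function, estrogen level, folate, and urine pregnancy test". Section 2.4 places it about four weeks after treatment starts.

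The Visit 1 paragraph of 2.4 does not mention estrogen, but the summary of lab panels that closes 2.4 does, as do 4.3.3 and the schedule in 5.9. Eligibility (4.3.4, 4.3.5) has no cycle-regularity criterion. Randomization is stratified by age and fibroids only.

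**The concern.** Estradiol varies with the menstrual cycle, so a change in it can be interpreted only if the cycle day at both ends is known or fixed. The plan leaves both ends open. Someone programming the analysis could reasonably carry the screening reference over from the EGCG clause. One woman's change would then start from menses and another's from mid-cycle or the luteal phase. If Visit 4 were taken as the end point, its phase would depend on each woman's cycle length.

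Two consequences follow. In the comparison of arms, phase variation inflates the spread, and with about 12 women per arm a chance imbalance in screening day can create or hide a difference. In the descriptive tables, within-arm changes from screening mix menstrual phase with drug effect. The reported SDs and interquartile ranges would include phase as well.

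The plan already collects two samples tied to cycle day, one on each side of the add-on course, but does not name them as the contrast.

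**Working it through.** **1. The plan's own figure.** The only computed figure is the ANOVA power of 0.44 and 0.85 at effect sizes 0.25 and 0.40 (36 women, alpha 0.05). With a noncentral F distribution and λ = N × f², λ = 36 × 0.0625 = 2.25 and 36 × 0.16 = 5.76. The treatment effect (2 and 30 df) then has power 0.229 and 0.521. The stated pair is matched by the treatment effect with 72 women (0.443 and 0.853). That is a separate matter and the present point does not depend on it; 0.521 serves below as a reference value.

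**2. The four samples side by side.**

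| Sample | Timing | Tied to cycle day? | Clomiphene/letrozole | EGCG |
|---|---|---|---|---|
| Screening | any cycle day | no | before | before |
| Visit 1 | cycle day 3 ± 2 | yes | before | already taking |
| Visit 2 | cycle day 8-10 | yes | after the course, as 4.3.3 describes it | taking |
| Visit 4 | day 30-35 | no | after | taking |

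All arms take EGCG, so the arms differ only in the add-on drug. Visits 1 and 2 bracket that drug.

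**3. Cycle phase at Visit 4.** Assume days are counted from day 1 of the Visit 1 cycle and that cycle length is L. The cycle day of study day d is ((d − 1) mod L) + 1. For d = 30 to 35:

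- L = 24: cycle day 6-11
- L = 28: cycle day 2-7
- L = 32: cycle day 30-32, or 1-3 of the next cycle
- L = 35: cycle day 30-35, before the next menses

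Visit 4 can therefore fall anywhere from late luteal to late follicular phase.

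**4. Variance of the candidate outcomes.** The documents give no estradiol SD or correlation. Assumptions, on the log scale: within-phase SD 0.4 (variance 0.16), correlation between visits 0.3 (covariance 0.3 × 0.16 = 0.048), and an independent phase component at screening with SD 0.5 to 0.8 (variance 0.25 to 0.64). The outcome visit is Visit 2 throughout.

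- Change from Visit 1: 2 × 0.16 × (1 − 0.3) = 0.224
- Change from screening: 0.224 + 0.25 = 0.474, up to 0.224 + 0.64 = 0.864
- Visit 2 adjusted for Visit 1: 0.16 × (1 − 0.3²) = 0.146
- Visit 2 adjusted for screening: 0.16 − 0.048²/0.41 = 0.154, up to 0.16 − 0.048²/0.80 = 0.157
- Visit 2 alone: 0.16

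Between the two change scores, the variance ratio is 0.474/0.224 = 2.1 to 0.864/0.224 = 3.9. The corresponding interval is √2.1 = 1.5 to √3.9 = 2.0 times as wide.

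Between the two adjusted analyses, the interval is only √(0.154/0.146) = 1.03 to √(0.157/0.146) = 1.04 times as wide with screening as covariate. Adjustment alone, even on screening, brings 0.474-0.864 down to 0.154-0.157. Choosing Visit 1 as the covariate takes it to 0.146.

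The ratio of the Visit 1 change score to the Visit 1-adjusted analysis is 2/(1 + correlation). It is 2.0 at correlation 0, 1.54 at 0.3 and 1.25 at 0.6, so adjustment is never the less precise of the two in this setting.

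**5. What that means for power, as an illustration.** Let k be the added phase variance divided by the remaining variance of the change, so that the effect size shrinks to f/√(1 + k). Step 4 gives k = 0.25/0.224 = 1.1 to 0.64/0.224 = 2.9. For f = 0.40, power is 0.52 at k = 0, 0.28 at k = 1 and 0.16 at k = 3.

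**6. Limit of the calculation.** It covers phase variance in the baseline sample only. Phase variance in an outcome sample, as at Visit 4, is not removed by adjusting for Visit 1. It is not quantified here.

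**The case against.** A reader might infer that the plan defines the estradiol change as screening to Visit 4. It does not. The screening reference sits in the EGCG clause, which also names Visits 1 and 2, and a Visit 1 to Visit 2 change is fully open under the present wording. What stands is that the contrast is undefined.

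A reader might also infer that random screening phase biases the comparison of arms. It does not in expectation: screening precedes randomization, so the effect is added variance and chance imbalance, and the ANOVA error term already reflects that variance. Bias through Visit 4 would require the add-on drugs to alter cycle length, and the documents give no data on that.

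Third, one might credit the ratio of 2.1 to 3.9 to the choice of baseline visit under the proposed analysis. That ratio compares two raw change scores. Once the baseline enters as a covariate, the choice of visit changes the interval by only about 3-4%.

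There are also limits to what Visit 1 can do. It is not a pre-EGCG baseline; screening is the only one. Visit 4 is the only estradiol sample after Visit 2, so leaving it out of the main contrast sets aside any later add-on effect. Menstrual history is scheduled at screening only, so the cycle day at Visit 4 may not be recoverable from what is now collected. All of this stands, and the fix allows for it.

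Finally, estradiol is one of several secondary outcomes in a study that describes itself as mainly descriptive and underpowered for formal inference. That limits the consequence. It does not remove the need to define an outcome that the plan nevertheless puts through an ANOVA.

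**Conclusion.** The point holds in a limited form. Sections 2.7 and 6.4 compare estradiol changes between arms without naming a baseline or an end visit and without adjustment. A change built on screening or on Visit 4 carries menstrual-phase variance. Between arms this costs precision and allows chance imbalance; within arms, a change from screening mixes phase with drug effect.

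Under the assumptions in step 4, none of which comes from the documents, the adjusted analysis has variance 0.146. That compares with 0.224 for a change from Visit 1 and 0.474 to 0.864 for a change from screening. Most of the gain comes from covariate adjustment. The Visit 1 sample is still the better covariate, because it is tied to cycle day and falls before the add-on drug. The sampling times and the missing definition can be read directly from the documents; only the size of the gain depends on assumptions. The change is worth making for a secondary outcome, but the primary pharmacokinetic comparison is unaffected.

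**What to change.** In 2.7 and 6.4, define the between-arm estradiol comparison as Visit 2 estradiol (cycle day 8-10) with Visit 1 estradiol (cycle day 1-5, before clomiphene or letrozole, all women already on EGCG) as covariate, alongside treatment and fibroid status. State the scale; the figures above assume logs.

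Keep screening and Visit 4 estradiol as descriptive summaries by arm, each reported with cycle day. Identify screening as the only pre-EGCG sample, and note that within-arm changes from it include menstrual phase.

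No new sample or visit is needed. The covariate costs one error degree of freedom (36 − 6 = 30 becomes 29 with the interaction in the model). A last-menses date may have to be added to the case report form at Visit 4. The main contrast will not address add-on effects that appear after Visit 2; the Visit 4 summaries will be the only information on those.
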